2.1 OBJECTIVES AND SCIENTIFIC AIMS

The aim of this prospective phase II trial is to evaluate the efficacy and confirm the safety of 5'-azacitidine after allogeneic T cell depleted (TCD) hematopoietic stem cell transplant (HSCT) from histocompatible matched or mismatched related or unrelated donor in patients with Myelodysplastic syndrome (MDS) and Acute Myelogenous Leukemia (AML) who are at high risk for relapse.

Primary objective:

To evaluate whether maintenance treatment post transplant with 5-azacitidine can reduce the relapse rate over the current standard of care for high-risk MDS and AML patients.

Secondary objectives:

1. To assess overall survival from the time of 5-azacitidine initiation.
2. To confirm the safety and tolerability of low dose 5'-azacitidine by measuring the frequency of transfusions, frequency of bleeding, frequency of serious infections, and use of G-CSF support.
3. To evaluate graft function and myeloid and T cell chimerism after administration of low dose 5'-azacitidine
4. To evaluate the incidence of acute and chronic GvHD following the initiation of 5-azacitidine.

Correlative Objectives:

Correlate treatment with low dose 5'-Azacitidine with:

1. Gene specific methylation in the hematopoietic stem cell (HSC) compartment in CD 34 cells subpopulations.
2. Recurrence of cytogenetic abnormalities in the hematopoietic stem cell (HSC) compartment in CD34 cells subpopulations.
3. Normalization of myeloid progenitor frequencies known to be altered in MDS.
4. Level of regulatory T cells (CD4+CD25-FoxP30).

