3.6 Correlative studies

Methylation- Although, in their study, De Lima et al did not demonstrate an effect on DNA methylation using unfractionated marrow cells it is possible that the shorter period of treatment (4 cycles) as well as lower average doses (16-40mg/m²) were responsible for that.

In this proposed study, the gene specific methylation in sorted hematopoietic and leukemic stem cells from marrow samples will be analyzed at several points: at diagnosis (if available), prior to transplant, posttransplant prior to initiation of 5'-azacitidine and every 3 months. The purpose to this part of the study is to determine if maintenance 5'-Azacitidine post transplant has an effect on methylation.

Minimal Residual Disease (MRD)- Currently there is still no one acceptable test with high specificity and sensitivity for detection of minimal residual myeloid disease. We plan to assess disease status by morphologic evaluation and immunophenotyping.

Moreover, In collaboration with [name] and [name] PhD, a panel of aberrantly expressed cell surface proteins that are highly specific and sensitive for the detection of cells bearing these antigens will be used to assess for residual MDS/AML cells. This will allow us to determine whether persistence of cells bearing these antigens can predict for relapse after transplant. This analysis will be performed by multi-parameter flow cytometry.

Cytogenetic changes in the stem cells- In collaboration with [name] PhD, and [name] fluorescence activated cell sorting (FACS) and FISH technique will be used to assess for residual involvement of the HSC compartment following transplantation, assessing for the effect of 5'-azacitidine therapy on residual MDS HSC over serial time points (e.g. every three months).

Graft-versus-Leukemia- Last, we'll assess the effect of 5'-Azacitidine on T cell differentiation with specific interest on Tregs. This will be done by the flow cytometry lab and will be part of routine post transplant "FLOW7 BMT" which assess for CD4, CD8 and CD19. In addition, the effect of treatment with post transplant 5'-Azacitidine on T regs will be studied.

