9.1 TREATMENT/INTERVENTION PLAN

1. 5'-azacitidine will be given at a dose of 32mg/m² for 5 consecutive days subcutaneously. Treatment will be given every 28 days (cycle). Treatment will be given up to a year post transplant.
2. CBC will be checked weekly during the first 2 cycles, and if stable every 2 weeks with following cycles. CBC results from tests performed externally will be accepted for Days 8, 15, and 22 of C1 and C2 and Day 15 of subsequent cycles. Comprehensive metabolic panel will be checked at the beginning of every cycle.
3. Pregnancy test will be checked for women at child bearing age prior to start of each cycle.
4. Bone marrow studies (day 100, and 6, 12, 18 and 24 months post transplant) for assessment of disease status and chimerism. Peripheral blood chimerism status at day 100, and 6, 12, 18 and 24 months post transplant will be tested as part of routine post transplant evaluation
5. Peripheral blood lymphocytes phenotyping and in-vitro response to standard panel of mitogen will be assessed as part of routine post transplant assessment
6. Bone marrow samples for correlative studies will be tested at the same time that patients are undergoing routine BM studies. These tests are considered experimental.
7. Peripheral blood samples for correlative studies will be collected prior to start of Azacitidine treatment on C1D1 and at 12 and 18 months post transplant. These tests are considered experimental.

Dose modifications

Event	Modification
ANC <1000/uL for > 4 days.	Drug held until resolved (ANC 1500) and up to 60 days. If after 60 days there is no neutrophils recovery the treatment will be permanently discontinued.
• If by next cycle ANC is 1000-1500, not G-CSF dependent	Resume therapy with 50% dose reduction
• If by next cycle ANC fully recovered, >1500 not G-CSF dependent	Resume full therapy dose
Platelets <10,000/uL for > 4 days, or if transfusion dependent to keep count>10,000/ uL	Drug held until resolved (>50,000) and up to 60 days.

• If by next cycle Platelets are 10,000-50,000, not transfusion dependent	Resume therapy but with 50% dose reduction
• If by next cycle Platelets >50,000	Resume full therapy dose
Hemoglobin < 8g/dL for > 4 days or if transfusion dependent	Drug held until resolved (> 8g/dL) and up to 60 days.
• If by next cycle hemoglobin >8g/dL	Resume full therapy dose
Hepatic toxicity – Drug related grade 3-4	Drug stopped

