10.0 EVALUATION DURING TREATMENT/INTERVENTION

During the treatment patients will be seen in clinic every 4 weeks (prior to every cycle) and more frequently if required by primary BMT attending. All patients will be closely monitored and evaluated as per MSKCC BMT standard of care guidelines. Evaluations may be withheld if the treating physician feels that there is a strong contra-indication to perform the study (e.g. patient has relapsed or is terminally ill). Also, additional tests will be performed as clinically indicated. Study specific assessment schedule listed in table below.

Schedule of Study Assessments

Procedures	Pre-Treatment	Post Treatment Start					
		C1 & C2			C3+		
		D1	D8	D15	D22	D1	D15
Window	45	(+/-) 7	(+/-) 3	(+/-) 3	(+/-) 3	(+/-) 7	(+/-) 3
Eligibility	X						
Informed consent	X						
History/Physical	X						
Pregnancy Test (1)	X	X					X
Blood Chemistry/CMP (2)	X	X					X
CBC (2)	X	X	X	X	X	X	X
Echo- if no new symptoms, pretransplant is adequate	X						
Toxicity assessment (3)		X				X	
Correlative studies – Peripheral blood for Tregs expression studies (4)		X*					

Procedures	Post Transplant				
	100 days	6 months	12 months	18 months	24 months
Window	(+/-) 21	(+/-) 14	(+/-) 14	(+/-) 14	(+/-) 14
Chimerism (Peripheral Blood) (5)	X	X	X	X	X
Bone marrow aspirate and/or biopsy (6)	X	X	X	X	X
Peripheral blood lymphocytes phenotyping and in-vitro response (7)	X	X	X	X	X
Correlative studies - BM sample for methylation assays, flow studies for MRD (8)	X	X	X	X	X
Correlative studies – Peripheral blood for Tregs expression studies			X	X	

*Peripheral blood samples will be collected prior to start of Azacitidine treatment on C1D1 only

- (1) Pregnancy Test – Not required for Cycle 1 Day 1 if done at screening, but required for Day 1 of each subsequent cycle for FCBP.
- (2) CBC – checked weekly during the first 2 cycles, and if stable, every 2 weeks with subsequent cycles. Outside CBC results will be accepted for D8, 15 and 22 of C1 and C2 and for D15 of subsequent cycles. CBC/Chemistry must result prior to IP administration on or within 7 days of Day 1 of each cycle. If a CBC is performed within overlapping windows for two time-points, it is not necessary to repeat unless clinically indicated.

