Treatment-related mortality	6 in the first 16 patients 7 in the first 20 patients 8 in the first 25 patients 9 in the first 29 patients 10 at any point	0.4	0.93
-----------------------------	---	-----	------

In addition to the primary endpoint, there are a number of secondary and correlative objectives.

Secondary Objectives:

1. Kaplan-Meier methodology will be used to compare overall survival.
2. The safety will be described by tabulating the number of transfusions, frequencies of bleeding and serious infections, and the use of G-CSF support.
3. We will also evaluate the following metrics: graft function; myeloid and T-cell chimerism; and acute and chronic GVHD incidence. Graft function will be examined after enrollment by summary statistics of hemoglobin levels, neutrophils and platelets. Myeloid and T-cell chimerism will be summarized as a continuous measurement at enrollment, 6, 9,12,18 months post-transplant and 24 months post-transplant. Cumulative incidence function will be used to estimate grade II-IV acute GVHD and chronic GVHD incidence.

Correlative Studies:

1. The global DNA methylation status will be evaluated at baseline, and the change from baseline will be explored among individuals who do and do not relapse by the 24 month BM evaluation. This continuous measurement will be compared using a rank-sum test.
2. The reoccurrence of cytogenetic abnormalities will be evaluated in the CD34 subpopulation of cells at the time of trial enrollment. This exploratory measure is calculated as the proportion of involved cytogenetic cells out of the total number of stem cells and may be a marker of disease burden following transplant. This proportion will be categorized and relapse will be contrasted across these categories using a permutation-based logrank test.
3. The composition of myeloid progenitor cells will be compared pre- and post- 5'-azacitidine treatment to explore whether normalization occurs following treatment. These paired measurements will be compared using McNemar's test.
4. The levels of regulatory T-cells and CD8+ will be graphically displayed across baseline and post-treatment time points.

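### The only planned methylation analysis compares relapsers with non-relapsers on global change, so it cannot show whether methylation changed after azacitidine and leaves the gene-specific objective without an analysis

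*Combined protocol and SAP*

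**What the plan says.** **Objective and purpose.** Section 2.1 sets out to correlate low-dose azacitidine with "Gene specific methylation in the hematopoietic stem cell (HSC) compartment in CD 34 cells subpopulations". Section 3.6 plans gene-specific analysis in sorted stem cells and gives the aim: "The purpose to this part of the study is to determine if maintenance" azacitidine alters methylation. Section 1.0 adds an interest in methylation and relapse risk.

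**Analysis.** Correlative item 1 of Section 14.1 is the only methylation analysis. It takes the global measure, and of that measure it says: "the change from baseline will be explored among individuals who do and do not relapse by the 24 month BM evaluation". On method it says: "This continuous measurement will be compared using a rank-sum test". It gives no alpha, no sidedness, no post-baseline time point, and no rule for the sample a relapsed patient contributes.

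**Assays.** Footnote 8 to the schedule in Section 10.0 lists global and gene-specific methylation. Section 10.1 describes a method for the global assay only.

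**Samples.** Sections 9.1, 10.0 and 10.1 schedule marrows at day 100 and at 6, 12, 18 and 24 months post transplant; Section 3.6 says every 3 months. Section 8.1 accepts any pre-treatment marrow as baseline. Drug starts between days 60 and 120 (Section 4.3), and on its end Section 9.1 says: "Treatment will be given up to a year post transplant". Under Section 10.0 the treating physician may withhold evaluations for a strong contra-indication, one example being that the "patient has relapsed or is terminally ill".

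**The concern.** There are two separate problems.

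First, the test does not match the question. Whether methylation changes on treatment is a within-patient question. The planned test asks whether the change differs between two outcome groups, and asks it of the global measure only. Carried out exactly as written, the plan would report nothing on correlative objective 1.

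Second, the change is undefined. With up to five scheduled post-transplant marrows per patient and no rule for choosing among them, the analyst must decide after the data are in. Some natural choices would compare groups that differ in time since the last dose and in whether the sample was taken at relapse. A difference could then appear even if early methylation change has no link to later relapse.

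**Working it through.** **1. Group sizes, from the plan's own design.** Section 14.1 gives N = 32, relapse proportions of 35% (unpromising) and 15% (promising), a limit of 7 relapses, and errors of 0.08 and 0.10. Exact binomial check:

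- Type I: P(X ≤ 7 | n = 32, p = 0.35) = 0.0818
- Type II: P(X ≥ 8 | n = 32, p = 0.15) = 0.0958

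Both agree with the plan. The rank-sum groups would then be:

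| Relapse scenario | Relapsers | Non-relapsers |
|---|---|---|
| 15% | 32 × 0.15 = 4.8, about 5 | about 27 |
| Decision limit | 7 | 25 |
| 35% | 32 × 0.35 = 11.2, about 11 | about 21 |

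The last row needs some relapses after accrual has ended, because accrual closes once more than 8 patients relapse.

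**2. What the rank-sum test can see.** Let the mean change be d + e in relapsers and d in non-relapsers. Adding d to every value leaves all ranks unchanged, so the test responds to e and never to d. Section 3.6 asks about d.

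The documents give no variance or alpha. The simulations below assume normal changes with SD 1, two-sided 0.05, and a usable sample from every patient.

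| Groups | Rejection rate, e = 0 (any d) | Power, e = 1 SD | e for 80% power |
|---|---|---|---|
| 5 v 27 | 4.6% | 47% | about 1.5 SD |
| 7 v 25 | 5.2% | 60% | about 1.3 SD |
| 11 v 21 | 4.7% | 70% | about 1.2 SD |

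**3. What a paired test would see.** Under the same assumptions, a signed-rank test of a 0.5 SD mean change has power of about 80% with 32 pairs, 64% with 25 and 54% with 20. So for a common change of 0.5 SD in all 32 patients, the planned test rejects at about its nominal 5% and the paired test at about 80%.

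**4. Timing of the scheduled marrows.**

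- Off drug: treatment ends by 12 months, so the 18-month marrow is at least about 18 − 12 = 6 months off drug and the 24-month marrow at least about 24 − 12 = 12 months.
- Cycles completed by about day 180: (180 − 60)/28 = 4.3 for a day-60 start and (180 − 120)/28 = 2.1 for a day-120 start, so about 2 to 4.
- Cycles by day 365: (365 − 60)/28 = 10.9 and (365 − 120)/28 = 8.75, in line with the 8–10 in Section 4.3.
- Day 100 with its 21-day window covers days 79 to 121. It is on treatment for a day-60 start and pre-treatment for a day-120 start.

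**5. Consequences of the unnamed marrow.**

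- Last available marrow: non-relapsers followed to 24 months would be measured about 12 months off drug. A first-year relapser would be measured on or shortly after drug, possibly with blasts in the sample.
- 24-month marrow: those who complete treatment and provide the sample are all long off drug, and relapsers' values may be missing or reflect relapse.
- A named pre-relapse marrow during or at the end of treatment: neither problem arises in this form.

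**The case against.** The strongest reply has four parts.

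- **The relapse comparison has a stated aim.** Section 1.0 names methylation and relapse risk. This stands: the comparison belongs in the plan, but it does not replace the within-patient analysis.
- **Bias is not built into the text.** A reader might infer that the follow-up sample is whatever exists up to 24 months, so that the analysis necessarily mixes drug effect, relapse and time off drug. Section 14.1 does not say so: the 24-month evaluation qualifies relapse, not the sample. A reader might also infer that relapsers have either no later marrow or one containing the relapsed clone. That is not generally true. A patient relapsing at 14 months can have day-100, 6-month and 12-month marrows from before relapse; relapse can be extramedullary (Section 12.1); and withholding is discretionary. Assaying sorted cells also limits contamination by bulk blasts, although it does not exclude clonal stem cells. This stands, so the confounding is conditional on the sample chosen.
- **Six months alone may be too early.** Only about 2 to 4 cycles are complete by then, and Section 3.6 suggests that 4 cycles may have been too few in the earlier phase I post-transplant study. This stands against 6 months as the sole time point.
- **A paired test in a single arm does not isolate the drug.** Post-transplant recovery may also shift methylation. This stands as a limit on interpretation, but the planned analysis gives no estimate of change at all.

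**Conclusion.** The point holds in a limited form. Two gaps are plain from the text and need no assumption: no analysis tests whether methylation changed after treatment, and none uses the gene-specific measure named in correlative objective 1. A third is also plain: the marrow defining the change is not named. That this would bias the relapse comparison is a possibility under the last-available or 24-month reading, not something the documents establish.

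The power figures rest on assumed normal data, SD 1, two-sided 0.05 and complete sampling. They illustrate scale and do not predict. With about 5 to 11 relapsers, the relapse comparison is reliable only for large differences (about 1.2 to 1.5 SD) even when every sample is available.

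The consequence is confined to the correlative conclusions. The analysis is exploratory, no decision rule uses it, and the sample size of 32 and the primary endpoint are untouched. This is an improvement worth making, not a defect in the trial's main inference.

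**What to change.** (a) Add to Section 14.1 a within-patient signed-rank test of change from the pre-treatment marrow, for both gene-specific and global methylation, at prespecified marrows already scheduled during or at the end of treatment (for example 6 and 12 months post transplant), using only samples taken before relapse. State which pre-treatment marrow is the baseline when there is more than one.

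(b) Keep the relapse comparison, but relate the change at one named marrow to later relapse among patients relapse-free at that marrow. Show the off-drug 18- and 24-month samples descriptively.

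(c) Reconcile Section 10.1 (global assay only) with Section 3.6 and the schedule footnote (gene-specific), and the every-3-months sampling in Section 3.6 with the schedule.

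**Cost.** No new visits or marrows. Section 14.1 needs rewording, and Section 10.1 may need a gene-specific method and the genes to be studied, which the documents do not list. Patients who relapse before the landmark leave the relapse comparison. An earlier landmark keeps more of them but reflects fewer cycles; a later one does the reverse. The paired result describes patients still relapse-free at the sample, and the report should say that it cannot separate drug effect from post-transplant recovery.

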6.1 CRITERIA FOR SUBJECT ELIGIBILITY

Patients who have undergone T cell depleted allogeneic hematopoietic stem cell transplantation at MSKCC for:

1. De novo myelodysplastic syndromes (MDS): IPSS-1 with poor risk cytogenetics or higher IPSS.
2. Acute myelogenous leukemia (AML) in first remission that required more than 1 cycle of treatment to achieve remission or with the following cytogenetic abnormalities: FLT3 mutation, deletion/monosomy of chromosome 5 or 7, MLL gene rearrangement, or more than or equal to 3 cytogenetics abnormalities. Also patients in second or greater remission.
3. Patients with Secondary MDS/AML.
4. Patients will be considered eligible for the study if after transplant they achieved hematologic (<5% blasts) and cytogenetic remission.
5. Patients will be eligible to enter the study between 60-120 days post transplant.

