6.3 Subject Exclusion Criteria

Patients will be excluded from the trial if at time of enrollment:

1. Active uncontrolled bacterial, fungal or viral infection.
2. Evidence of uncontrolled graft-versus-host disease.
3. Pulmonary: new onset hypoxia
4. Known or suspected hypersensitivity to 5'-azacitidine or mannitol.
5. Evidence of residual disease either by increased blasts count (>5%) or persistence of previous known cytogenetics abnormalities.
6. Peripheral blood neutrophil chimerism: less than 95% donor.

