14.1 BIOSTATISTICS

This phase II trial will explore the efficacy of treating high-risk MDS and AML patients with 5'-azacitidine following TCD-HSCT. Based on historical MSKCC data for patients with advanced MDS and AML (adults and pediatrics) with high relapse risk, who meet the entry criteria, the two-year

cumulative incidence of relapse is 35%. Therefore, this intervention would be considered promising if the two-year relapse proportion is 15% or less. If the relapse proportion is 35% or greater, the 5-azacitidine intervention would not be considered promising. Therefore, using a single stage exact design, a total of 32 patients will accrue on study. At the end of the trial, if seven or fewer patients relapse by two years post treatment initiation, the trial will be considered promising. If, however, more than 8 patients relapse at any point the study will be considered unpromising and will be closed for further accrual. The type I and type II errors for this trial are 0.08 and 0.10, respectively. It is anticipated that enrollment will be completed in 5 years with an accrual of approximately 6-7 patients/year.

If a patient is found to be ineligible for reasons unrelated to disease relapse or progression, or is lost to follow-up, s/he will be replaced for the primary endpoint. If a patient dies for reasons unrelated to disease relapse or progression (i.e., treatment related mortality), s/he will remain as part of the 32 patient cohort. Treatment-related mortality will be monitored as part of the stopping rules discussed below.

In order to reduce patient risk and confirm the safety of 5'-azacitidine in this setting, the study design includes early termination in event of severe neutropenia, severe thrombocytopenia, and treatment-related mortality. The boundaries are based on accrual of 32 patients. The calculations in the table below are based on marginal probabilities.

Failure Type	# of failures needed to stop the study	Failure rate in the population	Probability boundary is crossed
Neutropenia (Grade III-IV)	3 in the first 8 patients 4 in the first 14 patients 5 in the first 20 patients 6 in the first 27 patients 7 at any point	0.1	0.1
		0.3	0.92
Thrombocytopenia (Grade III-IV)	3 in the first 8 patients 4 in the first 14 patients 5 in the first 20 patients 6 in the first 27 patients 7 at any point	0.1	0.1
		0.3	0.92
	3 in the first 5 patients 4 in the first 8 patients 5 in the first 12 patients	0.15	0.07

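### The CD34 cytogenetic proportion is to be cut into unspecified categories before a permutation log-rank test; ranking it would usually keep more power and leave no cut-point to choose (minor)

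*Combined protocol and SAP*

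**What the plan says.** Section 14.1, Correlative Studies item 2, takes a measure that "will be evaluated in the CD34 subpopulation of cells at the time of trial enrollment" and is "calculated as the proportion of involved cytogenetic cells out of the total number of stem cells". It then states: "This proportion will be categorized and relapse will be contrasted across these categories using a permutation-based logrank test". The number of categories, the cut-points, when they are chosen, and whether the permutation covers that choice are not given there or elsewhere. The item calls the measure exploratory and attaches no significance level or power to it.

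Item 1 of the same list keeps its marker, global methylation, continuous and uses a rank-sum test.

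Two eligibility rules bear on the values. Section 6.3 item 5 excludes patients with "Evidence of residual disease either by increased blasts count (>5%) or persistence of previous known cytogenetics abnormalities". Section 6.1 item 2 admits, among others, "Acute myelogenous leukemia (AML) in first remission that required more than 1 cycle of treatment to achieve remission", as well as patients with a FLT3 mutation or in second or later remission.

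On size, section 14.1 says "using a single stage exact design, a total of 32 patients will accrue on study", with two-year relapse of 35% as the unpromising rate and 15% as the promising one.

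**The concern.** The measure is a proportion. Sorting patients into groups treats everyone in a group as alike, and with so few relapses the trial can ill afford to lose that information. No reason is given for cutting this marker when methylation is left uncut.

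Leaving the cuts open also affects the validity of the p-value. A permutation p-value is valid if the grouping was set without sight of the relapses, or if the choice of grouping is repeated inside every permutation. The plan commits to neither.

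There is also a gap about who can be measured. Some routes into the trial do not require a chromosome abnormality, so some patients may have nothing for FISH to count. The plan does not say how they enter this analysis.

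At stake is whether a candidate marker of residual disease is missed, or reported on the strength of a favourable cut.

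**Working it through.** **1. The plan's own figures.** With 32 patients and seven or fewer relapses counted as promising, P(X ≤ 7 | 32, 0.35) = 0.0818 and P(X ≥ 8 | 32, 0.15) = 0.0958. These match the stated 0.08 and 0.10. No figure is stated for the cytogenetic analysis.

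**2. Expected relapses.** 32 × 0.15 = 4.8 and 32 × 0.35 = 11.2, so about 5 to 11. Accrual also closes once more than 8 patients relapse, so 11 is near the top of what this analysis could have.

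**3. Information kept by a cut.** Assume a normal marker with log-hazard linear in it. A two-group cut at c, with a fraction p below it, keeps R = φ(c)² / [p(1 − p)] of the log-rank information.
- Median: 0.3989² / 0.25 = 0.64.
- Quartile: 0.3178² / 0.1875 = 0.54.
- 90th percentile: 0.1755² / 0.09 = 0.34.
- Tertiles (three groups): 2 × 0.3636² / (1/3) = 0.79.

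If the uncut test had 80% power at two-sided 5%, power after a two-group cut is Φ(√R × 2.80 − 1.96). This gives 61% (median), 54% (75th percentile) and 37% (90th). Tertiles on 2 degrees of freedom give 60%.

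**4. Simulated power at the trial's size.** Settings: n = 32, exponential relapse times, two-year censoring, normal marker, permutation log-rank with 399 permutations, 2,000 trials per row. Assumptions, because the documents give none: two-sided 5%, hazard ratio (HR) of 2 to 4 per SD, no competing deaths.

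| Relapse | HR | Raw value | Ranks | Median split | Top quartile | Tertiles |
|---|---|---|---|---|---|---|
| 15% | 2 | 0.301 | 0.270 | 0.100 | 0.244 | 0.178 |
| 15% | 3 | 0.558 | 0.518 | 0.198 | 0.444 | 0.370 |
| 15% | 4 | 0.704 | 0.665 | 0.252 | 0.576 | 0.491 |
| 25% | 2 | 0.438 | 0.406 | 0.250 | 0.360 | 0.290 |
| 25% | 3 | 0.762 | 0.730 | 0.464 | 0.626 | 0.554 |
| 25% | 4 | 0.884 | 0.864 | 0.623 | 0.770 | 0.722 |
| 35% | 2 | 0.565 | 0.530 | 0.372 | 0.398 | 0.357 |
| 35% | 3 | 0.895 | 0.874 | 0.667 | 0.741 | 0.690 |
| 35% | 4 | 0.963 | 0.952 | 0.820 | 0.873 | 0.862 |

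Relative to ranks, the smallest loss is 1 − 0.873/0.952 = 8%. Setting aside the median split at 15% relapse, the largest is 1 − 0.250/0.406 = 38%. For the median split at 15% relapse the loss is about 62% (for example 1 − 0.198/0.518). Part of that loss comes from discreteness: with about five events, the permutation median split rejects only 2.2% of the time when there is no association.

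**5. False positives with no association, nominal 5%.**

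| Rule for the cut | 15% relapse | 25% | 35% |
|---|---|---|---|
| Fixed (median, top quartile, tertiles) | 0.022-0.046 | 0.036-0.043 | 0.050-0.058 |
| Best of three quartile cuts, uncorrected | 0.094 | 0.103 | 0.124 |
| Best of all cuts from 4/28 to 28/4, uncorrected | 0.262 | 0.307 | 0.339 |
| Best of all cuts, search repeated in each permutation | 0.060 | 0.052 | 0.055 |
| Ranks, no cut | 0.054 | 0.043 | 0.057 |

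**6. A marker with many zeros.** The cytogenetic exclusion makes zeros plausible. With 50-85% zeros and an assumed HR of 5, none-versus-any was compared with the raw value.
- If risk rises with level, none-versus-any loses: 0.736 falls to 0.272 (50% zeros, 15% relapse), or 0.726 to 0.599 (85% zeros, 25% relapse).
- If only presence matters, none-versus-any mostly gains: 0.511 rises to 0.635 (70% zeros, 25% relapse).

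A further check used a marker bounded between 0 and 1, 0-75% zeros and 15-35% relapse. Ranks beat a median split in every setting where risk rises with level (for example 0.34 v 0.18, 0.43 v 0.21, 0.69 v 0.52). Where only presence matters, ranks lost at most about 0.09 to none-versus-any, while the raw value lost up to 0.28 (0.33 v 0.61). This is why ranks are preferred to the raw value.

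**7. Who can be measured.** Sections 3.6 and 10.1 describe sorting by FACS followed by FISH, which needs an abnormality to look for. Entry under section 6.1 through a FLT3 mutation, through slow first remission, or in later remission does not require one. Section 3.1 itself notes that many AML patients have no prognostically specific cytogenetic change. The number affected cannot be derived from the documents.

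**The case against.** The strongest reply has four parts.

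- **The measure is labelled exploratory.** No decision, safety rule or error rate depends on it. This stands and settles the severity.
- **Cutting can be sensible for a marker that is mostly zero.** If the presence of residual clone is what matters, none-versus-any beats the raw value. This stands against the raw value. It has little force against ranks, which lose at most about 0.09 there and gain where level matters.
- **The power losses depend on inputs the documents do not give.** This also stands. A reader might infer that grouping discards most of the information or always halves power. It does not: a median cut keeps 64% of the information and tertiles 79% under step 3, and most fixed cuts in step 4 lose well under half the power.
- **Nothing says the cuts will follow the data.** This is correct. A reader might infer that the planned test carries a false-positive rate of 26-34%. That would need an uncorrected search for the best cut. Fixed cuts hold their size, and so does a search repeated inside the permutation. What remains is that the plan does not commit to either.

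A reader might also infer that patients with no chromosome marker will be scored zero and placed in the lowest category. No section says so; their handling is simply unstated. Nor is it certain that most values will be zero. Section 6.3 excludes "persistence of previous known cytogenetics abnormalities", but section 12.1 treats the FACS and FISH results as separate and experimental, so they may be positive in a patient who met the entry criteria.

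**Conclusion.** The point holds as a minor one. The plan commits to categorizing a quantitative marker, gives no cut-points, and expects about 5 to 11 relapses. Where risk rises with level, a fixed grouping typically loses about 10-40% of the power, and half or more in unfavourable cases such as a median split at 15% relapse. Uncorrected data-driven cuts could raise a nominal 5% false-positive rate to 9-12% or, at worst, 26-34%. That is a risk left open by silence, not a stated procedure.

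The sizes assume two-sided 5%, an HR of 2 to 4 per SD, a normal marker, log-linear risk and no competing deaths. The direction is firmer than the sizes: ranks did better than a median split in every setting tested where risk rises with level, and gave up little where only presence matters. The primary decision is unaffected.

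**What to change.** Amend Correlative Studies item 2 in section 14.1 before relapse data are examined:

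1. Keep the permutation log-rank framework, but use the ranked proportion as the score (midranks, with zeros tied).
2. If a grouped display is wanted, such as none versus any detected, fix it in advance. Otherwise, state that the cut search is repeated inside each permutation.
3. Limit the test to patients with a chromosome abnormality that the FISH assay can track, and report how many are left out.

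The cost is a few sentences of wording and no new data. There are two downsides: slightly less power than none-versus-any if only presence matters, and the loss of patients without a trackable abnormality from this one analysis. How many that is, and how many relapses go with them, is not known from the documents.
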